**Dietary Education Intervention with Wechat Model Will  
Impact on Dietary Protein Intake in Patient Treated  
With Peritoneal Dialysis**

NCT: 02426580

April 30, 2017

Study Design

Study Type: (select one)
 
 Clinical Interventional       Clinical Interventional
 
 Non-clinical (i.e., benchwork, in-vitro, animal model)       Other (explain):

Does the proposed research require an Investigational New Drug (IND)/Investigational Device Exemption (IDE) application (US), a Clinical Trial Application (CTA) (Canada and EU), and/or any other similar regulatory filing?
 
 Yes       No      Explain the basis for your determination: we have cell phones and free download software of wechat

Pathology, disease state, or condition to be treated/studied and incidence:
 
End-stage renal disease (ESRD) patients were treated with peritoneal dialysis. The peritoneal dialysis prescription: 3-4 daily exchanges of 2L dialysate, 16-24 hours a day. Dialysate: 1.5% or 2.5% glucose in dialysate and the concentration of calcium in dialysate is 1.25mmol/L.

Study Population (ages, gender, relevant disease states):
 
Age of 18 to 65 years and no limitation of sex. The patients were diagnosed as ESRD.
 
Key Inclusion Criteria: 1. All patients followed at the PD center that successful completed training and have received treatment for at least 1 month. 2. The life expectancy will be more than one year. 3. All patients will provide written informed consent. (1) Aged between 18 and 65 years old; (2) had been on PD for more than one month in medically stable condition; (3) no peritonitis within one month; (4) All the participants or their family members were required to own a Smartphone and to be able to correctly complete the follow up consultations either on Wechat or on phone calls.
 
Key Exclusion Criteria: 1. the patients will be severe ill status and unlikely to survive for 12 months.

Duration of subject participation: 1st December 2014 – 31st December 2017
 
Prospective : April 2015 to April 2017
 
Retrospective: January 2014 to January 2015


Total number of subjects to be enrolled: We will enrolled 140 PD patients from the Stern peritoneal dialysis unit in the Third People's Hospital of Chengdu affiliated with Chongqing Medical University
 
Number of study or comparison groups: All patients will be assigned into two groups according to their willing.
 
Intervention group: N=70
 
Controlled group: N=70

Specific details of Treatment/Intervention: (prescription and/or therapy, devices, equipment, solutions, product to be used in conducting study):
 
This will be a 12-month, A combined prospective and retrospective study of dietary education intervention with comprehensive peritoneal dialysis education with emphasis on egg whites based optimal protein intake on Wechat platform compared with a conventional clinic visit education model. At enrollment, patients will be educated with the conventional education model including operation of dialysate, the catheter exit care, complications of PD, record of ultrafiltration and urine volume, basic protein intake (egg white will be added as a

suitable kind of protein intake) and calorie intake. And then they will be randomly assigned into one of two parallel groups: (1) Control group: Intervention with conventional education every 1-3 months during routing clinical visit ;( 2) Intervention group: wechat delivery of dietary education: Intervention with conventional education will occur every 3 months during routing clinical visit and wechat model of dietary education will occur every 1 month by cellphone. The control group will also receive monthly cell phone calls but without the wechat intervention. The wechat model will provide information on protein, calcium, phosphorus and sodium intake, suggested by the current KDIGO/ KDOQI guideline. The wechat model will include pictures, words, video and voice. Furthermore, we will emphasize the use of egg white protein which may be effective dietary component lowering serum phosphorus without risking malnutrition. The baseline characteristics included the following variables : age, sex, diabetes, cause of kidney disease if known, medication list, comorbid condition list, smoking history, body weight (kilograms), blood pressure , PCR, serum albumin, serum total protein, C-react protein(CRP)、 white blood cell count(WBC), hemoglobin, serum phosphorus, serum calcium, serum sodium, serum magnesium, serum uric acid, intact parathyroid hormone (iPTH), vitamin D, bicarbonate, KT/V, WCC. The study period will be 12 months, with the patients returning every 3 months for measurement of parameters, peritoneal equilibration test (PET), calculation of KT/V and WCC by software, dietary interviews and 3 day dietary recall and conventional education of PD. And we will record the incidence of peritonitis, readmission and switching to hemodialysis and mortality rate. During the course of study, the dose and types of medication could be changed if medically necessary in the view of the treating physician.

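### Inclusion criterion (4) accepts phone-call ability in place of WeChat ability, so the stated rule does not ensure that a patient assigned to the WeChat arm can receive the WeChat education

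*Combined protocol and SAP*

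**What the plan says.** Under Key Inclusion Criteria, item (4) applies to every participant or a family member. They must "own a Smartphone and to be able to correctly complete the follow up consultations either on Wechat or on phone calls". The item does not tie either mode of contact to a study group.

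Under Specific details of Treatment/Intervention, conventional education comes first, and then the text says: "And then they will be randomly assigned into one of two parallel groups". For the intervention group, "wechat model of dietary education will occur every 1 month by cellphone", and "The wechat model will include pictures, words, video and voice". For the comparison group, "The control group will also receive monthly cell phone calls but without the wechat intervention".

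Under Number of study or comparison groups, the method of assignment is different: "All patients will be assigned into two groups according to their willing". The planned enrolment is 70 per group.

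Neither the protocol nor the SAP describes a check of WeChat ability, a substitute means of delivery for WeChat-arm patients who cannot use it, or a rule for analysing them. WeChat ability is not among the baseline variables listed in the protocol or the SAP.

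**The concern.** The ability clause in criterion (4) is the only part of the eligibility text that touches on whether a patient can take part remotely, and phone ability is enough to satisfy it. A phone call can carry voice but not pictures, text or video. Taken as written, the rule therefore admits households for which the tested intervention may not be deliverable, and nothing later in the plan catches this.

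The consequence depends on how patients reach their group. With random assignment, some phone-only households would land in the WeChat arm. The average difference between groups would shrink and power would fall. With assignment by preference, phone-only households would mostly stay with the controls. Dilution then largely disappears, but the groups are sorted by WeChat ability, which the plan does not record and so could not examine or adjust for.

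**Working it through.** **Step 1: the text side by side.**

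- Entry: smartphone in the household, plus ability to complete follow-up consultations by WeChat or by phone call. This applies to all participants, with no arm named.
- WeChat arm: monthly education with visual and spoken content on WeChat.
- Control arm: monthly phone calls without WeChat.
- Sequence: the intervention section places random assignment after the enrolment education, so eligibility is settled before the arm is known.

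A household able to use WeChat meets the entry rule and can receive either arm's contact, provided it can also take calls. A household able only to take calls meets the same entry rule but may be unable to receive the WeChat arm's content.

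**Step 2: the plan's sample size.** The section on whether the study is sufficiently powered gives a difference of 0.090 g/(kg.d), an SD of 0.154 from 10 pilot patients, and 50 per group. It states neither the power nor whether the test is two-sided. With n = 2[(z_alpha + z_beta) × 0.154/0.090]²:

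- two-sided 0.05: 46 at 80% power, 50 at 83%, 62 at 90%
- one-sided 0.05: 37 at 80%, 51 at 90%

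So 50 is reached two-sided at about 83% power. A two-sided test is assumed below.

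**Step 3: dilution.** Let f be the share of the WeChat arm that cannot use WeChat and gains nothing. The documents give no value for f, so it is an assumption. The mean difference becomes 0.090 × (1 − f). With the SD held at 0.154, power = Φ(d / (0.154 × √(2/n)) − 1.96).

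The standard error is 0.154 × √(2/50) = 0.0308 at 50 per group and 0.154 × √(2/70) = 0.0260 at 70. The middle column uses 56 per group, which is 70 less the plan's 20% dropout (70 × 0.8).

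| f (assumed) | Mean difference | Power, 50 per group | Power, 56 per group | Power, 70 per group |
|---|---|---|---|---|
| 0 | 0.090 | 0.832 | 0.871 | 0.933 |
| 10% | 0.081 | 0.749 | 0.795 | 0.875 |
| 20% | 0.072 | 0.647 | 0.696 | 0.790 |
| 30% | 0.063 | 0.534 | 0.581 | 0.677 |

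One entry in full: f = 20%, n = 70 gives 0.072/0.0260 = 2.77; 2.77 − 1.96 = 0.81; Φ(0.81) = 0.79.

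The number per group for 80% two-sided power rises from 46 at f = 0 to 57, 72 and 94 at f = 10%, 20% and 30%.

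**Step 4: the other assignment rule.** If patients choose their group, f in the WeChat arm is probably near zero and the table hardly applies. The documents give no figure from which to size the resulting self-selection.

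**The case against.** The strongest reply is that the clause is loose wording with a harmless meaning: the patient or a family member can handle whichever mode is used. It covers all participants, names no arm, and asks everyone for a smartphone, which phone calls alone would not need. That reading is fair. But the text joins the two modes with an either/or and specifies no check, so it does not secure the harmless meaning.

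Second, inability is not established. Every eligible household has a smartphone, a family member may be the user, and the protocol describes WeChat as free and convenient. The clause also concerns completing consultations, while the intervention is largely messages sent to patients. This stands as a limit on the likely size: the number affected may be small. It does not close the gap, because no criterion secures ability to receive the messages either.

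Third, assignment by willingness would remove most of the dilution. This stands. It makes the random-assignment statement a condition of the power figures, and the contradiction between the two statements is the larger issue.

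Fourth, 50 per group is a pessimistic base when 70 are planned. This also stands, so the result at 70 is given first in the verdict.

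A reader might go further and infer that criterion (4) is applied by arm, with WeChat ability asked of one group and phone ability of the other, so that the groups are different populations even under sound randomisation. The two modes do match the two arms' contacts, but nothing in the protocol or SAP says that eligibility is judged or re-applied by arm, or that patients are moved between groups. It is a risk that the wording leaves open, not a procedure in the plan.

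Finally, the document is dated April 30, 2017 and gives the prospective period as April 2015 to April 2017, so a new screening rule may come too late for patients already enrolled.

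**Conclusion.** The point holds as a modest gap in a stated rule. Criterion (4) accepts phone ability as sufficient, and nothing before or after assignment checks that WeChat-arm patients can receive the intervention.

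Under random assignment, and if an assumed 10%, 20% or 30% of that arm gained nothing, power falls from about 93% to 88%, 79% or 68% at 70 per group before dropout, and from about 83% to 75%, 65% or 53% at 50 per group. These figures assume a two-sided 0.05 test, an SD of 0.154, and that 0.090 is the effect in patients who can use WeChat, which the plan does not say. The share affected is unknown and could be close to zero, so the documents do not support a statement that the trial is underpowered for this reason.

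Under assignment by willingness, the issue is self-selection by WeChat ability, of unknown size. Different eligibility by arm is only a possibility that clearer wording would remove.

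**What to change.** Reword criterion (4) as one rule for all participants, confirmed before assignment: the patient, or the family member who will receive the messages, can use WeChat on a smartphone and can also take the monthly calls. Phone ability then becomes an additional requirement, not an alternative. A test message at screening is one way to confirm this; the method is a matter of choice.

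State that patients are analysed in the group to which they were assigned. Reconcile the two statements on assignment (by willingness, or at random), since the meaning of the comparison depends on which was used.

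If enrolment is already complete, the rewording cannot change who entered. The report should then say how criterion (4) was applied, how patients were assigned, and, where records allow, how many WeChat-arm patients could not use WeChat.

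The cost is a short protocol change and a brief check with free software the trial already uses. The downside is that some phone-only households are excluded and the result applies to WeChat-capable households.

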#### **Efficacy Assessments (What data will be collected/utilized?):**

Wechat is available and convenient for all kinds of platforms with a little network traffic fee (less than 10 RMB per month); enjoy group chat and private chat; support voice, photo, video and text messages. Baidu search found that at present 600 million people had registered wechat in China. We will use the software of wechat to send message to our PD patients with the Nutrition knowledge of protein, phosphorus, calcium and sodium. And the messages will be picture or/and video of food model with voice or/and words notes. Egg whites are tasty and readily available with a low phosphorus content and could be a good source for additional protein intake for the PD patients. The outcomes of our study may be the following:(1) The protein intake of PD patients will achieve or be close to the target of 1.2g/kg/d in intervention with wechat group; (2) Changes in parameters of primary endpoints from baseline to last evaluation may be show significant difference between the intervention with wechat group and the control group; (3) The incidence of peritonitis, readmission, switching to hemodialysis and mortality rate may be lower in the intervention with wechat group compared with the control group. Furthermore the limitations of our study are the single center design.

#### **Statistical Methods (for analyzing primary & secondary endpoints):**

Continuous variables are reported as mean $\pm$ SD. Categorical variables are reported as frequency and percentage. Comparisons between values of intervention with wechat group and values of controlled group at every time points of study will be made. Continuous variables with normal distribution will use analysis of t-test. Continuous variables with abnormal distribution will use analysis of rank-sum test. Categorical variables will use analysis of covariance. Regression analysis will be performed to comparing the levels of primary endpoints, with PCR being the independent variable. Logistic regression analysis will be performed within the secondary endpoints. All statistical tests were conducted at a significance level of  $\alpha = 0.05$ . All the statistical analyses will be conducted with Empower Stats.

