**Is the study sufficiently powered (adequate sample size) to answer the research question? Explain:**

We tested a sample population of 10 patients treated at the PD center who successfully completed training and were on therapy for at least 3 months. At the time of the first clinic visit, we collected data and calculated mean  $\pm$  SD of PCRs as  $0.834 \pm 0.154$  using SPSS (version1.6). According to sample size counting formula  $N = 2^*[(\alpha+\beta)^*\sigma/\delta]^2$ , we calculated that a total sample size of 50 patients in each group will be needed to detect a significant difference ( $P<0.05$ ) in PCR of  $+0.090$  g/(kg.d) from baseline to last measurement during the study between the wechat group and control group. The sample size (assuming a 20% dropout rate) was estimated at 60 patients in each group. So we think this study is sufficiently powered to answer the research question.

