**Statistical Analysis Plan (SAP)**

1. Analysis of baseline parameters, including: age, sex, body weight (kilograms), nPCR, serum albumin, hemoglobin, serum phosphorus, serum calcium, intact parathyroid hormone (iPTH), KT/V, WCC, dietary protein intake(DPI), dietary energy intake(DEI) and the protein provided by the egg white.
2. Analysis of parameters after 12 months, including: body weight (kilograms), nPCR, serum albumin, hemoglobin, serum phosphorus, serum calcium, intact parathyroid hormone (iPTH), KT/V, WCC, dietary protein intake(DPI), dietary energy intake(DEI) and the protein provided by the egg white.
3. Analysis of the difference of the incidence of peritonitis, readmission and switching to hemodialysis or renal transplant and lost follow-up.

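### The regression planned for the primary endpoints has PCR as predictor and no group term, so it does not estimate the WeChat effect; the planned group test uses unadjusted values while the target is stated as change, and no main analysis is named

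*Combined protocol and SAP*

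**What the plan says.** - **Regression.** Statistical Methods: "Regression analysis will be performed to comparing the levels of primary endpoints, with PCR being the independent variable". No dependent variable, group term or PCR time point is given.
- **Group test.** The same section: "Comparisons between values of intervention with wechat group and values of controlled group at every time points of study will be made", by t-test if the variable is normal and by rank-sum test if not. No covariate is named for this test.
- **Target of the trial.** Efficacy Assessments, outcome (2): "Changes in parameters of primary endpoints from baseline to last evaluation may be show significant difference". The sample size section takes a PCR difference of 0.090 g/(kg.d) "from baseline to last measurement during the study between the wechat group and control group".
- **Source of the SD.** The sample size section: "At the time of the first clinic visit, we collected data and calculated mean", followed by 0.834 ± 0.154 in 10 patients. This is the SD of single values.
- **SAP item 2.** "Analysis of parameters after 12 months, including: body weight (kilograms), nPCR" and other parameters. No model or contrast is attached. Item 1 lists nPCR at baseline.
- **Primary endpoints.** The term is used but never defined. The sample size rests on PCR, while outcome (1) in Efficacy Assessments is about dietary intake: "The protein intake of PD patients will achieve or be close to the target of 1.2g/kg/d in intervention with wechat group".
- **Allocation.** The entry on the number of groups says "All patients will be assigned into two groups according to their willing". The intervention section says that patients are randomised to two parallel groups.

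**The concern.** The only model written for the primary endpoints does not address the question on which the trial is sized. If PCR is a predictor and group is absent, the coefficient describes an association across all patients, whichever arm they are in. The word independent may be a slip for dependent, but no group term is named on either reading.

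That leaves the t-test or rank-sum test to carry the WeChat comparison. It is specified for values, whereas the aim is described as change. The two differ in power and in how they treat a baseline difference between arms. Visits are every 3 months for 12 months, and neither a visit nor an analysis is marked as the main one. The result to be emphasised could therefore be chosen after the data are seen. The planned test also makes no use of baseline nPCR, which is collected in any case.

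**Working it through.** **1. The plan's own figure.** N per group = 2[(z_α + z_β)σ/δ]², with σ = 0.154 and δ = 0.090. Neither sidedness nor power is stated.

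- One-sided 0.05, 90% power: 2[(1.645 + 1.282) × 0.154/0.090]² ≈ 50.2, which matches the stated 50 (51 if rounded up).
- Two-sided 0.05, 80% power: 2[(1.960 + 0.842) × 0.154/0.090]² ≈ 46.

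The match to 50 is inferred. Two-sided 0.05 is assumed below.

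**2. What the regression as written measures.** Two simulated cases, 50 per arm, PCR SD 0.154, with an illustrative outcome:

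- No WeChat effect on PCR, outcome depends on PCR: the slope on PCR is significant in 100% of runs, the group t-test on PCR in 5.1%.
- True WeChat effect of 0.090 on PCR, outcome unrelated to PCR: the slope is significant in 5.1%, the group t-test in 81%.

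The slope does not track the WeChat effect in either direction.

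**3. Three ways to make the group comparison.** Let ρ be the correlation between baseline and 12-month nPCR. The documents give none, so 0.3, 0.5 and 0.7 are assumed. The SDs are:

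- 12-month values: 0.154.
- Changes: 0.154√[2(1 − ρ)] = 0.182, 0.154, 0.119.
- Regression on group with baseline covariate: 0.154√(1 − ρ²) = 0.147, 0.133, 0.110.

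Power is from the noncentral t with noncentrality 0.090/(SD√(2/n)). It has 2n − 2 degrees of freedom, or 2n − 3 with the covariate. For values at n = 50, the noncentrality is 0.090/(0.154 × 0.2) = 2.92.

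| Analysis, 50 per arm | ρ = 0.3 | ρ = 0.5 | ρ = 0.7 |
|---|---|---|---|
| Values | 82.5% | 82.5% | 82.5% |
| Changes | 68.6% | 82.5% | 96.2% |
| Baseline covariate | 85.8% | 91.6% | 98.2% |

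The 95% CI half-width is 0.061 for values and 0.058, 0.053, 0.044 with the covariate. At 48 per arm (60 less 20%), values give 80.9% against 84.4%, 90.5%, 97.8% with the covariate. At 56 per arm (70 less 20%), the figures are 86.5% against 89.5%, 94.3%, 99.0%.

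**4. How firm the SD is.** With 10 patients and normality, the 95% CI for the SD is 0.106 to 0.281. Power of the values test at 50 per arm then runs from 0.99 to 0.35. At both limits the covariate model is at least as powerful as the other two at each ρ.

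**5. If patients chose their group.** Assume a baseline gap of 0.045, no true effect and 50 per arm. Simulated false-positive rates at ρ = 0.3, 0.5, 0.7 are:

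| Case | Values | Covariate model | Changes |
|---|---|---|---|
| Arms regress to a common mean | 7/11/17% | 5% | 14/11/9% |
| Gap stays stable | about 30% | 18/13/9% | 5% |

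In the stable case the covariate model is biased by 0.045(1 − ρ) = 0.0315, 0.0225, 0.0135. Neither it nor the change score holds 5% in both cases.

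**The case against.** **The trial has a WeChat contrast without the regression.** This stands. A reader might infer that the plan contains no test of the WeChat effect. It does: the group comparison at every time point, with nPCR at 12 months listed in the SAP. Statistical Methods never claims that the PCR regression estimates the WeChat effect, and relating other endpoints to PCR is a legitimate secondary question. It is still the only model given for the primary endpoints, and nothing ranks it against the group test.

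**The plan does say what is tested.** A reader might infer that it leaves open whether values or changes are compared. Statistical Methods says values, and SAP item 2 is consistent with that. The change wording sits in an expected outcome and a sample size rationale, neither of which is an analysis instruction. The defect is a mismatch between the stated target and the stated test.

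**The covariate model is optional under randomisation.** This stands as far as validity goes. The t-test is valid, and at ρ = 0.3 the gain is only from 82.5% to 85.8%. The gain costs almost nothing, however, since baseline nPCR is already collected.

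**The bias figures rest on another problem.** They do. The contradiction over allocation is a separate defect and adds no weight here. If patients chose their group, the covariate model does not cure the bias.

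**Conclusion.** The point holds in this form. The regression for the primary endpoints cannot estimate the WeChat effect on PCR. The planned group test is of unadjusted values, while the target is described as change from baseline. No main analysis or primary time point is named. This should be fixed, but it does not invalidate the trial.

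Under random allocation the loss from the unadjusted test at 50 per arm is about 3, 9 and 16 percentage points of power at ρ = 0.3, 0.5 and 0.7. These differences depend on the assumed correlations, on two-sided 0.05 and on an SD from 10 patients, so the ordering of the methods is firmer than the absolute levels. The false-positive rates apply only if patients chose their group, and they also assume the 0.045 gap. Taking nPCR as the primary endpoint is an inference from the sample size section, because the documents do not define the primary endpoints.

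**What to change.** 1. Have the sponsor confirm that nPCR is the primary endpoint.
2. Replace the regression sentence in Statistical Methods with:

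> The main analysis is a linear regression with 12-month nPCR as dependent variable, study group as independent variable and baseline nPCR as covariate; the group coefficient is reported with its 95% CI. The unadjusted t-test or rank-sum comparison of 12-month values is supportive. Any regression of other endpoints on PCR is exploratory.

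3. State whether the last evaluation (Efficacy Assessments) and the last measurement (sample size section) both mean the 12-month visit.
4. Reconcile the two statements on allocation, as a separate matter. If patients chose their group, add baseline covariates already collected (for example age, sex, diabetes, KT/V) and report the comparison of change in nPCR as a sensitivity analysis. State also that neither model removes bias in every case.

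The cost is a few sentences and, if patients chose, one extra analysis. All variables are already collected, so no new visits or patients are needed.

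### Logistic regression, the apparent method for peritonitis and readmission, ignores unequal time at risk and discards repeat episodes; if exits differ by arm, peritonitis shifts against the arm observed longer

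*Combined protocol and SAP*

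**What the plan says.** Two sentences in the Statistical Methods section bear on the clinical events. One sets the reporting: "Categorical variables are reported as frequency and percentage". The other sets the model: "Logistic regression analysis will be performed within the secondary endpoints". The same section assigns analysis of covariance to categorical variables, which does not suit yes/no events.

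The events appear in three places. The details of the intervention say that "we will record the incidence of peritonitis, readmission and switching to hemodialysis and mortality rate". The Efficacy Assessments section gives the expected direction: "The incidence of peritonitis, readmission, switching to hemodialysis and mortality rate may be lower in the intervention with wechat group". Item 3 of the Statistical Analysis Plan reads "Analysis of the difference of the incidence of peritonitis, readmission and switching to hemodialysis or renal transplant and lost follow-up"; death is not in that item.

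On follow-up: "The study period will be 12 months, with the patients returning every 3 months". The sample-size section enlarges the groups "assuming a 20% dropout rate", without splitting that figure by arm or cause.

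None of these sections defines incidence as a proportion or as a rate over patient-time. None mentions an offset, censoring, competing events, a rule for repeat episodes, or whether observation continues after a patient leaves PD.

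**The concern.** An ever/never outcome gives each patient the same weight however long that patient was observed. Someone who leaves PD at month 2 without peritonitis counts the same as someone free of it for all 12 months. Switch to hemodialysis, transplant, death and loss to follow-up each end the observed risk of PD peritonitis, yet the plan treats them only as outcomes to compare.

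This matters because the plan hopes that WeChat will reduce both peritonitis and two of the exits (switch and death). If the hope about exits is met, WeChat patients accrue more time in which peritonitis can be seen, and success on one endpoint works against the test of another. Peritonitis and readmission can also recur, and a logistic model keeps only the fact of at least one episode.

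**Working it through.** **The plan's own figure.** The only computed figure is the PCR sample size. With σ = 0.154 and δ = 0.090, 2 × [(1.645 + 1.282) × 0.154/0.090]² ≈ 50, so 50 per group is reproduced at one-sided 5% and 90% power. This is one possible reading, since power and sidedness are not stated. It has no bearing on the events, for which the plan gives no figure.

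**Inputs from the documents.** Follow-up of 12 months; 20% dropout overall; 70 per arm ("Intervention group: N=70", and the same for control).

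**Assumptions.** Peritonitis rate λ of 0.2 to 1.0 per patient-year, the same in both arms. Exits p of 10% to 40%, by arm. Constant hazards, with exit independent of peritonitis. Patients who leave without an event are kept in the model as non-events.

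**Formulas.** Exit hazard μ = −ln(1 − p). Proportion with a first episode by 12 months: P = λ/(λ + μ) × [1 − exp(−(λ + μ))].

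**Worked case: λ = 0.4, exits 30% control and 10% WeChat.**
- Control: μ = 0.357, P = 0.4/0.757 × (1 − 0.469) = 28.1%.
- WeChat: μ = 0.105, P = 0.4/0.505 × (1 − 0.603) = 31.4%.
- Odds ratio = (0.314/0.686)/(0.281/0.719) = 1.17.
- Person-time rate: 0.281/0.701 = 0.40 and 0.314/0.785 = 0.40, so the rate ratio is 1.00.

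**Odds ratio, WeChat to control, with no true difference (exits WeChat v control):**

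| λ per year | 20% v 20% | 10% v 20% | 10% v 30% | 10% v 40% |
|---|---|---|---|---|
| 0.2 | 1.00 | 1.07 | 1.15 | 1.25 |
| 0.4 | 1.00 | 1.08 | 1.17 | 1.29 |
| 0.6 | 1.00 | 1.09 | 1.20 | 1.33 |
| 1.0 | 1.00 | 1.12 | 1.27 | 1.44 |

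For exits of 10% v 20% or 10% v 30%, the proportions differ by about 1 to 6 percentage points. With 70 per arm, a nominal 5% two-sided test rejects in about 5% to 11% of trials.

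**Check with another exit pattern.** Take λ = 0.30 and exits spread evenly over the year. A full-year patient has an episode with probability 1 − exp(−0.3) = 0.259; a leaver with 1 − 0.259/0.3 = 0.136. WeChat (10% exits): 0.9 × 0.259 + 0.1 × 0.136 = 24.7%. Control (30%): 0.7 × 0.259 + 0.3 × 0.136 = 22.2%. The odds ratio is 1.15.

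**When WeChat truly helps (rate ratio 0.80, control λ = 0.4).** With 20% exits in both arms, P is 24.7% v 29.8%, odds ratio 0.77. With exits of 10% v 30%, P is 26.1% v 28.1%, odds ratio 0.90.

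**Repeat episodes, full year, no exits.** The share of episodes kept is [1 − exp(−λ)]/λ. At 0.30 this is 0.259/0.30 = 86%, so 14% are lost. At 1.0 it is 0.632, so 37% are lost.

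**Hemodialysis switch as the event.** With switch hazards of 0.08 v 0.15 per year and other exits equal at 0.10 per year, the same formula gives 7.3% v 13.3%: the arm with fewer switches looks better. With equal switch hazards (0.10 or 0.15) and other exits of 10% v 20% or 30%, the odds ratio is 1.06 to 1.14.

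**The case against.** The case against has several parts.

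- **The link is inferred.** The plan does not say which endpoints are secondary, and an undefined incidence could mean episodes per patient-time. This stands as a caution. But logistic regression is the only named method that fits a yes/no event, and no rate or time-to-event method is offered.
- **The shift is conditional and modest.** It needs exits that differ by arm. The 20% is an allowance for the PCR comparison, and any split by arm is assumed. In the worked case the gap is 0.033 × 70 = 2.3 patients. This stands, and is why a range is shown. The loss of repeat episodes does not depend on it.
- **Leavers might be excluded instead.** The plan does not say. Under the independence assumed here, exclusion would remove the shift, but it would discard leavers' episodes and fail if peritonitis itself leads to exit.
- **Readmission differs from peritonitis.** A patient can be readmitted after a switch or transplant, so time on PD is the wrong denominator. This stands.
- **Confounding may matter more.** The study design table assigns groups by patients' wishes, while the intervention details say assignment is random. If wishes decide, confounding could exceed this bias, and an offset does not address it. That is a separate point.

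A reader might infer that the arm keeping patients on PD longer will look worse on all these events. The documents do not support that. With equal exits there is no shift; a true benefit may only be diluted; and an arm with fewer hemodialysis switches usually looks better on switching.

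**Conclusion.** The concern holds in limited form. The plan has no means of handling unequal time at risk, competing exits or repeat episodes, although it foresees dropout and hopes for fewer exits in one arm. For peritonitis, the effect is a shift against the arm with longer exposure if exits differ. It is small at a 10-point difference in exits, larger at 20 points, and absent with equal exits. In the example with a true rate ratio of 0.80, more than half of the apparent benefit on the odds-ratio scale disappears: 1 − 0.77 = 0.23 falls to 1 − 0.90 = 0.10. The loss of repeat episodes arises whatever the exits.

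These sizes rest on assumed rates, assumed exits by arm, constant and independent hazards, and leavers counted as non-events. No claim is made that longer PD time harms the switching result; there, the gap is that competing exits and censoring are not handled. The primary PCR comparison is unaffected, so this is a change the plan should make but not a fatal flaw.

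**What to change.** - Name the secondary endpoints, and define the incidence of peritonitis and readmission as episodes per patient-year, with all episodes counted.
- Compare arms by negative binomial or robust Poisson regression with group as a term. Use log time on PD in the study as offset for peritonitis and log observed follow-up time for readmission, and state whether follow-up for readmission continues after a patient leaves PD.
- Analyse hemodialysis switch by cause-specific hazard and by cumulative incidence, with death and transplant as competing events and loss to follow-up as censoring.
- Record the date of every episode and every exit, with its reason. The plan commits only to recording incidence, and without dates none of these analyses can be done.

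The cost is a revision of SAP item 3 and the logistic regression sentence, slightly more analysis work, and the recording of dates. The documents do not say whether those dates are already held; if not, they must be recovered from clinical records.
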